1.1 Objective

This study is designed to evaluate the effectiveness of adding a plano lens to weekend atropine after visual acuity has stabilized with weekend atropine but amblyopia is still present. Children ages 3 to <8 years with visual acuity of 20/50 to 20/400 in the amblyopic eye will be enrolled in a run-in phase with weekend atropine until no improvement, followed by randomization of eligible patients to weekend atropine treatment with a plano lens over the sound eye versus without a plano lens over the sound eye. The primary objective is to determine if adding a plano lens to weekend atropine will improve visual acuity in patients with amblyopia still present after visual acuity has stabilized with initial treatment.

1.2 Rationale for the Study

Amblyopia is the most common cause of monocular visual impairment in both children and young and middle-aged adults. Both patching and atropine are accepted treatment modalities for the management of moderate amblyopia in children.¹ Many practitioners prescribe weekend atropine as initial therapy for amblyopia. However, many children fail to achieve normal visual acuity in the amblyopic eye after treatment with this regimen. In a randomized trial conducted by PEDIG comparing atropine regimens, 58 of 83 patients with moderate amblyopia (70%) had amblyopic eye visual acuity of 20/32 or worse after 4 months of treatment with weekend atropine.² In another PEDIG randomized trial comparing atropine with a plano lens versus without a plano lens for initial treatment of amblyopia, 60 of 84 patients with moderate amblyopia (71%) had amblyopic eye visual acuity of 20/32 or worse after 16 weeks of treatment with weekend atropine.³ When improvement stops after initial therapy and amblyopia is still present, treatment options include increasing the dosage of current treatment, switching to another treatment, maintaining the same treatment and dosage, or combining treatments. Many clinicians will add a plano lens over the sound eye to atropine treatment, in part because families using atropine have become comfortable with its use. This option is limited to children with hypermetropia in the sound eye. However, it is unknown whether adding a plano lens over the sound eye will improve amblyopic eye visual acuity more than continuing atropine alone in patients who have shown no improvement after initial treatment with atropine. In a PEDIG randomized trial comparing patching to atropine for initial treatment of amblyopia, a plano lens was prescribed for the sound eye for 55 patients who had not improved to 20/30 or at least 3 lines after 4 months of daily atropine use.^{1,4} Their mean acuity improvement prior to using the plano lens was 1.0 line, compared with 1.6 lines after prescribing the plano lens. We are unaware of any reports of the response of treatment of amblyopia still present after initial treatment with weekend atropine.

1.3 Synopsis of Study Design

The study consists of two phases:

- 1) A run-in phase during which all patients are treated with atropine.
 - Patients may be enrolled either at the initiation of atropine treatment or during the course of treatment, provided that the prescribed treatment regimen to that point has been weekend or daily atropine.

- 46 2) A randomized trial, beginning after visual acuity has stabilized and amblyopia is still present, in
47 which the patient is randomized to either continue weekend atropine or to use a plano lens over
48 the sound eye with weekend atropine.
49

50 Major Eligibility Criteria for Run-in Phase (see section 2.2 for a complete listing)

- 51 • Age 3 to < 8 years
52 • Amblyopia associated with strabismus, anisometropia, or both
53 • Visual acuity in the amblyopic eye between 20/50 and 20/400 inclusive
54 • Visual acuity in the sound eye 20/32 or better and inter-eye acuity difference ≥ 3 logMAR lines
55 • Amblyopia treatment within the past 6 months subject to the following stipulations:
56 ➤ No more than 6 weeks of any amblyopia treatment other than spectacles (except for patients
57 being treated with atropine who are entering the study on treatment)
58 ➤ No *simultaneous* treatment with patching and atropine
59 ➤ No use of atropine in combination with the sound eye spectacle lens reduced by more than
60 1.50 D
61 ➤ Maximum level of treatment within the past 6 months:
62 ▪ Patching: up to 2 hours daily
63 ▪ Atropine: up to once daily
64 • Wearing spectacles with optimal correction (if amblyopic eye acuity is 20/80 or better, then VA
65 must be stable in glasses; if amblyopic eye acuity is 20/100 or worse, then spectacles and atropine
66 can be initiated simultaneously).
67 • Hypermetropia and spectacle correction in sound eye of +1.50 D or more
68

69 Eligibility Criteria for Randomization:

- 70 • Amblyopic eye acuity of 20/40 to 20/160 with an inter-ocular difference of ≥ 2 lines, or amblyopic
71 eye acuity of 20/32 with 3 lines of IOD.
72

73 Atropine Run-In Phase

74 At enrollment, patients will begin (or continue, in circumstances described above) weekend atropine,
75 and they will be followed every 6 weeks. Participation in this phase ends when there has been no
76 improvement of one or more lines in amblyopic eye acuity between 2 consecutive visits at least 6
77 weeks apart, confirmed by a re-test, and patients have received at least 12 weeks of atropine treatment.
78

79 Randomized Treatment Groups

80 When there has been no improvement with weekend atropine, eligible patients will be randomized to
81 one of two treatment regimens:

- 82 • Intensified treatment: Weekend atropine 1% with plano lens over the sound eye
83 • Control: Weekend atropine 1%
84

85 Sample Size

86 Seventy-nine patients will be randomized in each of the two treatment groups, for a total of 158
87 patients. This sample size has 90% power to detect a difference if the true difference in change from
88 baseline between groups is 0.075 logMAR at 10 weeks, with 2-sided type I error of 5%.
89

90 RCT Contact and Visit Schedule

- 91 • Phone call 5 weeks after randomization
92 • Primary outcome visit 10 weeks after randomization. Patients will return for an additional off-
93 atropine visit 2 weeks later.

- 94 • If amblyopic eye acuity improved by ≥ 1 line at primary outcome, follow-up visits at 10 week
95 intervals until no improvement, confirmed by a re-test
96

[figure not shown]
97 Primary Analysis

98 The primary outcome is amblyopic eye visual acuity 10 weeks after randomization.

99
100 The primary analytic approach for the amblyopic eye acuity will be a treatment group comparison of
101 the mean amblyopic eye acuity adjusted for baseline acuity using an analysis of covariance.
102

103 **1.4 Study Summary Flow Chart**

104

105

106

Chapter 2: Patient Enrollment

2.1 Eligibility Assessment and Informed Consent

A minimum of 158 patients are expected to be enrolled with a goal to enroll an appropriate representation of minorities. As the enrollment goal approaches, sites will be notified of the end date for recruitment. Patients who have signed an informed consent form can be randomized up until the end date, which means the minimum recruitment goal might be exceeded. The maximum number of randomized patients will be 178.

A patient is considered for the study after undergoing an eye examination by an investigator (as part of standard care) that identifies amblyopia meeting the eligibility criteria. As noted in subsequent sections, refractive error must be corrected with glasses (as per standard care) before a patient can be enrolled into the trial.

For patients who appear eligible for the study following a “standard-care” examination, the study will be discussed with the child’s parent(s) or guardian. Parents or guardians who express an interest in the study will be given a brochure and a copy of the consent form. Written informed consent will be obtained from the parent or guardian prior to performing any study-specific procedures that are not part of the patient’s routine care.

2.2 Eligibility and Exclusion Criteria

The following criteria must be met for the patient to be enrolled in the study:

1. Age 3 to < 8 years
2. Amblyopia associated with strabismus (comitant or incomitant), anisometropia, or both
 - Criteria for strabismus: At least one of the following criteria must be met:
 - Heterotropia at distance and/or near fixation on examination (with or without spectacles)
 - History of strabismus surgery
 - Documented history of strabismus which is no longer present (which in the judgment of the investigator could have caused amblyopia)
 - Criteria for anisometropia: At least one of the following criteria must be met:
 - ≥ 0.50 D difference between eyes in spherical equivalent
 - ≥ 1.50 D difference between eyes in astigmatism in any meridian
3. Amblyopic eye has no myopia (-0.25 D or more spherical equivalent).
4. Visual acuity, measured in each eye without cycloplegia (see exception for atropinized sound eye in section 2.3.2) within 7 days prior to enrollment using the ATS single-surround HOTV letter protocol as follows:
 - Visual acuity in the amblyopic eye between 20/50 and 20/400 inclusive
 - Visual acuity in the sound eye 20/32 or better
 - Inter-eye acuity difference ≥ 3 logMAR lines (i.e., amblyopic eye acuity at least 3 lines worse than sound eye acuity)
5. Amblyopia treatment within the past 6 months subject to the following stipulations:
 - No more than 6 weeks of any amblyopia treatment other than spectacles (except for patients being treated with atropine who are entering the study on treatment)
 - No *simultaneous* treatment with patching and atropine

- 152 • No use of atropine in combination with the sound eye spectacle lens reduced by more than 1.50
153 D
- 154 • Maximum level of treatment within the past 6 months:
155 ➤ Patching: up to 2 hours daily
156 ➤ Atropine: up to once daily
- 157 6. Spectacle correction for measurement of enrollment visual acuity must meet the following criteria
158 and be based on a cycloplegic refraction that is no more than 6 months old:
- 159 a. Requirements for spectacle correction:
- 160 1) Hypermetropia must not be undercorrected by more than +1.50 D spherical equivalent, and
161 the reduction in plus sphere must be symmetric in the two eyes.
- 162 2) Correction of the sound eye must have spherical equivalent of +1.50 D or more.
- 163 3) For patients meeting criteria for only strabismus (see 2.2 #2 above), spectacle correction is
164 otherwise at investigator discretion.
- 165 4) For patients meeting criteria for anisometropia or combined-mechanism (see 2.2 #2 above)
- 166 • Spherical equivalent must be within 0.50 D of fully correcting the anisometropia
167 • Cylinder power in both eyes must be within 0.50 D of fully correcting the
168 astigmatism
169 • Cylinder axis in the spectacle lenses in both eyes must be within 6 degrees of the
170 axis of the cycloplegic refraction when cylinder power is ≥ 1.00 D
- 171 b. For patients with enrollment acuity of 20/80 or better, spectacles meeting above criteria must
172 be worn either:
- 173 1) for 16 weeks immediately prior to enrollment, or
174 2) until visual acuity in amblyopic eye is stable (defined as two consecutive visual acuity
175 measurements by the same testing method at least 4 weeks apart with no improvement of
176 one line or more)
- 177 • An acuity measurement done any of the following ways may be considered the first
178 of two consecutive measurements: 1) in current glasses, 2) in trial frames with full
179 correction of hypermetropia with cycloplegia, or 3) in new glasses. *Note: since this*
180 *determination is a pre-study procedure, the method of measuring visual acuity is not*
181 *mandated.*
- 182 c. For patients with enrollment acuity of 20/100 or worse, initiating treatment with spectacles and
183 atropine simultaneously is allowed
- 184 7. No current vision therapy or orthoptics
- 185 8. No ocular cause for reduced visual acuity
- 186 • nystagmus per se does not exclude the patient if the above visual acuity criteria are met
- 187 9. Ocular examination within 6 months prior to enrollment
- 188 10. No prior intraocular or refractive surgery
- 189 11. No known allergy to atropine or other cycloplegic drugs
- 190 12. Down Syndrome not present
- 191 13. Parent willing to accept randomized treatment, has home phone (or access to phone), and willing to
192 be contacted by Jaeb Center staff
- 193 14. Parent does not anticipate relocation outside area of active study site

194

195 **2.3 Examination Procedures**

196 **2.3.1 Historical Information**

197 Historical information elicited will include the following: date of birth, gender, ethnicity, iris color,
198 prior amblyopia therapy (e.g., glasses, patching, pharmacologic, Bangerter filters), current spectacle
199 correction, and history of allergy to cycloplegic eye drops.

200

201 **2.3.2 Clinical Testing**

202 Examination procedures include:

203 1. Visual Acuity

- 204 • Measurement of visual acuity in each eye (right eye first) by the ATS single-surround HOTV
205 testing protocol.
- 206 • The ATS-HOTV visual acuity protocol must be used throughout the study. The protocol for
207 conducting the visual acuity testing is described in the ATS Testing Procedures Manual.
208 Aspects of the testing protocol that are specific to this study are:
 - 209 ➤ Testing of the amblyopic eye must be done without cycloplegia (with spectacles, if worn)
210 no more than 7 days prior to enrollment.
 - 211 ➤ Patients currently wearing spectacles must have amblyopic eye acuity measured while
212 wearing spectacles - trial frames or phoropter cannot be used.
 - 213 ➤ If the sound eye is atropinized, then the best-corrected (based on the most recent
214 refraction) sound eye visual acuity will be measured by placing the appropriate refractive
215 correction before the sound eye.

216 2. Ocular motility examination

- 217 • Measurement of alignment by Simultaneous Prism and Cover Test (SPCT) in primary position
218 at distance and near
- 219 • If performed within prior 7 days, it does not need to be repeated at time of enrollment

220 3. Ocular Examination

- 221 • Complete ocular examination, including dilated fundus examination, to rule out a cause for
222 reduced visual acuity other than amblyopia.
- 223 • If performed within prior 6 months, it does not need to be repeated at time of enrollment

224 4. Cycloplegic Refraction

- 225 • Cycloplegic refraction using cyclopentolate 1% as per investigator's usual routine
- 226 • If performed within prior 6 months, it does not need to be repeated at time of enrollment

Chapter 3: Atropine Run-In Phase

3.1 Atropine Run-In Phase Follow-up Visits

After enrollment, weekend atropine is prescribed. Those children using daily atropine at enrollment will be switched to weekend atropine. During the run-in phase, follow-up visits will occur every 6 weeks as long as both of the following criteria are met:

- Amblyopic eye has improved at least one line from the previous visit
- Amblyopia is still present, defined as amblyopic eye acuity at least one line worse than the best sound eye acuity that has been recorded at any visit during the study

Note: If the amblyopic eye acuity meets the above criteria, follow-up will continue every 6 weeks even if the sound eye acuity has worsened from the prior visit.

At each follow-up visit, visual acuity will be tested using the ATS HOTV visual acuity testing protocol with a study certified visual acuity tester. If the amblyopic eye acuity has not improved from the prior visit, acuity should be re-tested.

- If on the re-test there is still no improvement from the prior visit, and the prior visit was at least six weeks ago and the patient was on atropine for at least 12 weeks then the patient has completed the Atropine Run-In Phase of the study, otherwise, the patient continues in follow-up.
- The better of the two amblyopic eye visual acuities at the last visit of the Atropine Run-In Phase serves as the baseline amblyopic eye acuity for the Randomized Trial.

If a re-test is required and acuity improves on the re-test, then the re-test acuity serves as the value to which the next visit is compared when judging improvement.

Patients may be enrolled into the Atropine Run-In Phase either at the initiation of atropine treatment or during the course of treatment, provided that the prescribed treatment regimen to that point has been weekend or daily atropine.

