3.3 Patients Who Skip the Atropine Run-In Phase

Some patients will enter the randomized trial phase of the study without participating in the Atropine Run-In Phase. These patients must have met the same applicable criteria for eligibility (see sections 2.2 and 3.2.) and must have had no improvement in amblyopic eye visual acuity between 2 visits at

269 least 6 weeks apart using the ATS HOTV protocol, confirmed by a re-test. These patients must have
270 been treated for at least 12 weeks with weekend or daily atropine by a study investigator.

271

272 For patients who skip the Atropine Run-In Phase, visual acuity will be tested in each eye using the
273 ATS HOTV visual acuity testing protocol using a study certified visual acuity tester. The testing (and
274 re-testing to confirm no improvement) of the amblyopic eye must be performed without cycloplegia
275 and with the patient wearing spectacles if prescribed (i.e., trial frames cannot be used). The better of
276 the two amblyopic eye visual acuities will serve as the baseline acuity for the Randomized Trial. If the
277 sound eye is atropinized, then the best-corrected (based on the most recent refraction) sound eye visual
278 acuity will be measured by placing the appropriate refractive correction before the sound eye.

279

Chapter 4: Randomized Trial Phase

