4.4.2 Primary Outcome Visit

The primary outcome visit will occur at 10 ± 1 weeks. Atropine will be discontinued at this visit.

Testing will include the following:

1. Visual acuity

- Measured in each eye (right eye first) by a certified masked examiner using the ATS single-surround HOTV acuity protocol on study certified visual acuity tester.
- The best-corrected acuity of the atropinized sound eye will be measured by placing the appropriate refractive correction before the sound eye (e.g., using lenses in trial frames if needed)
- Children who were randomized to receive atropine plus a plano lens will be tested using their old glasses for the primary outcome exam and any additional exams.

2. Re-testing of visual acuity in the amblyopic eye (if indicated)

- If amblyopic eye visual acuity has not improved from randomization by at least one line, then it will be re-tested.
- The results of the re-test will be used only to determine if the patient will continue study participation with the same study-mandated treatment. The first visual acuity will be used as the primary outcome visual acuity. If neither the test nor the re-test is one line better than the visual acuity at randomization, then study participation ends after the post-primary outcome examination.

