6.1 Primary Analysis for Efficacy

The study is evaluating 2 management approaches for amblyopia in patients already treated with weekend atropine:

1. Continued weekend atropine 1%
2. Intensified treatment: Weekend atropine 1% with plano lens

The primary analysis will be a treatment group comparison of logMAR visual acuity scores obtained 10 weeks after randomization, adjusted for baseline acuity scores in an analysis of covariance (ANCOVA) model.

The primary analysis will follow the intent-to-treat principle. Data will be included only from patients who complete the 10-week outcome. There will be no imputation of data for patients who are lost to follow-up or withdraw from the study prior to the 10-week outcome. In a secondary analysis, imputation methods for missing data will be assessed (such as last-observation-carried-forward and multiple imputation) for consistency with the primary analysis. A separate analysis also will be conducted including only patients whose outcome exams were performed within the time window for the visit.

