6.2 Secondary Efficacy Analyses

6.2.1 Visual Acuity Defined as a Binary Outcome

A secondary analysis will be a treatment group comparison of the proportion of patients who have improved by 2 or more logMAR visual acuity lines 10 weeks after randomization for each treatment group, adjusted for baseline acuity scores using logistic regression.

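### Baseline is the better of two acuity tests and the 10-week outcome is a single test: within-arm gain is not on equal terms, and the mean of the two baseline tests would be a slightly better ANCOVA covariate

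*Protocol*

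**What the plan says.** **Baseline.** A patient leaves the run-in only when a test and a confirming re-test both fail to show improvement ("If on the re-test there is still no improvement from the prior visit", Protocol 3.1). Two readings therefore normally exist at that visit, and "The better of the two amblyopic eye visual acuities at the last visit of the Atropine Run-In Phase serves as the baseline" value for the trial. Section 3.3 says the same for patients who skip the run-in: the better of "the two amblyopic eye visual acuities will serve as the baseline acuity for the Randomized Trial".

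**Outcome at 10 weeks.** Section 4.4.2 makes the re-test conditional: "If amblyopic eye visual acuity has not improved from randomization by at least one line, then it will be re-tested". The re-test serves only the decision to continue; for analysis, "The first visual acuity will be used as the primary outcome visual acuity". The continuation decision lets either reading count: follow-up stops "If neither the test nor the re-test is one line better than the visual acuity at randomization".

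**Analysis.** The primary analysis (6.1) compares 10-week logMAR acuity between arms, "adjusted for baseline acuity scores in an analysis of covariance (ANCOVA) model". Section 6.2.1 compares the proportion "improved by 2 or more logMAR visual acuity lines 10 weeks after randomization". Section 6.2.2 repeats both analyses at the last study visit but does not say which reading is scored when a visit has two.

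**The concern.** The better of two noisy readings is, on average, better than a typical reading, while a single reading carries no such shift. Improvement from baseline to week 10 is therefore not measured like for like. Taken alone, this pulls mean gain and the 2-line rate down in both arms. Someone who reads the within-arm figures as the benefit of continuing atropine, with or without the plano lens, would be reading a number that depends partly on the test rule.

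There is also a question of efficiency. ANCOVA gains precision from a reliable covariate. Two readings are available, and their mean has less error than the better of the two.

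**Working it through.** **Inputs from the protocol (6.4, 1.3):** SD of change 0.14 logMAR, difference 0.075, two-sided alpha 0.05, power 90%, 5% loss, 79 per arm.

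**Assumptions not in the protocol:** single-test error SD *s* of 0.05 to 0.10 logMAR; SD of true acuity *τ* of 0.20 in the worked examples (0.15 was also tried); independent, normal test errors.

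**1. The plan's own figure.** n per arm = 2 × (1.960 + 1.282)² × 0.14² / 0.075² = 2 × 10.51 × 0.0196 / 0.005625 = 73.2, so 74. With the t distribution it is 75. Then 75 / 0.95 = 78.9, so 79 per arm and 158 in total. The figure is reproduced.

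**2. Error of each possible baseline.** For two independent errors of SD *s*:

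- Expected shift of the better one: s/√π = 0.564s toward good acuity. This is 0.028 at s = 0.05 and 0.056 at s = 0.10.
- Error variance: single test s²; better of two s²(1 − 1/π) = 0.682s²; mean of two 0.5s².
- The better-of-two value therefore has 0.682 / 0.5 = 1.36 times the error variance of the mean. It keeps 0.5 / 0.682 = 73% of the mean's precision and has 32% less error variance than one test.

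**3. Effect on the ANCOVA before the run-in filter.** Residual variance = A + τ²ν/(τ² + ν), where ν is the covariate's error variance and A is the part that the choice of covariate does not affect. Take s = 0.07 and τ = 0.20. Then ν = 0.00334 (better of two) or 0.00245 (mean), and A = 0.14² − 0.00334 = 0.01626.

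- Better of two: 0.01626 + 0.04 × 0.00334 / 0.04334 = 0.01934
- Mean: 0.01626 + 0.04 × 0.00245 / 0.04245 = 0.01857
- Ratio: 0.960

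**4. The same with the run-in filter.** Patients are randomized only if neither reading beats the prior visit, and this narrows the gap. Simulation with readings in 0.1 steps, τ = 0.20, 75 analysed per arm:

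| s | Residual SD, better of two | Residual SD, mean | Variance ratio | Power, better of two | Power, mean | Power, first test only |
|---|---|---|---|---|---|---|
| 0.05 | 0.1427 | 0.1415 | 0.983 | 89.2% | 89.7% | 88.3% |
| 0.07 | 0.1424 | 0.1406 | 0.975 | 89.3% | 90.0% | 87.7% |
| 0.09 | 0.1413 | 0.1390 | 0.968 | 89.8% | 90.7% | 87.4% |

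Applying the 3.1 rule over successive visits, with s from 0.05 to 0.10, gives about 2% to 3% lower residual variance and 0.4 to 1.2 points more power. The edges of the assumptions give 1.4% (s = 0.05, unrounded readings: 0.1389² / 0.1399² = 0.986) and just under 4%. The mean was the better covariate in every setting. The expected between-arm difference was 0.075 under every baseline.

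**5. Change from baseline and 2-line rates.** The filter also shifts the baseline the other way, because patients are selected for not testing better than before. With 0.1 steps and the rule applied over successive visits, the net shift is 0.013 to 0.025 logMAR toward good acuity for better-of-two (gain understated). It is 0.008 to 0.024 the other way for the mean (gain overstated). With a filter at one visit only, the figures are 0.006 to 0.009 and 0.014 to 0.030.

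2-line rates at s = 0.07 in the step 4 runs (no true gain in control, 0.075 in the intensified arm):

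- Better of two: 13.0% and 27.8%, difference 14.8 points
- Mean: 14.1% and 29.5%, difference 15.4 points

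The absolute rates depend on the baseline rule; the contrast between arms hardly does.

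**The case against.** The strongest defence is that nothing here is misstated. Each rule is explicit, the same in both arms, and fixed before randomization, and the trial's question is the difference between arms. That stands, and it limits the point to description and a little precision.

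A reader might infer more than the documents support:

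- **That the treatment effect is biased.** It is not. The primary analysis compares 10-week acuity between randomized arms, given a covariate measured identically in both.
- **That half of the baseline information is thrown away.** Both readings determine which is better. The better value keeps about 73% of the mean's precision and outperforms a single test.
- **That the week-10 rule should change to match.** The 10-week re-test is done only after a first test without a one-line gain. Scoring the better reading there would remeasure only apparent non-improvers. The first-test rule is sound.
- **That the mean should also be the baseline for change and 2-line outcomes.** Step 5 shows that this exchanges one bias for an opposite one of similar size, and which is smaller depends on assumptions. In simulation 40% to 49% of mean baselines also fell on half-lines. Outcomes move in whole lines, so for those patients the 2-line threshold would in effect become 2.5 lines.
- **That the last-visit analyses in 6.2.2 share the defect.** The protocol does not say which reading is scored there, and the statistical analysis plan may do so.

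**Conclusion.** The point holds in a limited form and is minor. The baseline and outcome rules differ, so within-arm change and absolute 2-line rates at 10 weeks are not absolute gain; regression to the mean after selection would affect them under any baseline. The arm comparison and the sample size are unaffected.

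The one available gain is in the covariate: about 2% to 3% less residual variance and roughly 0.4 to 1.2 points of power, from readings already taken. The sizes rest on an assumed single-test SD of 0.05 to 0.10 logMAR, since the protocol gives no test-retest figure. The direction of the precision gain held throughout the range tried; the size of the shift in within-arm change did not.

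**What to change.** 1. In 6.1, define the baseline covariate of the primary ANCOVA as the mean of the test and re-test at the randomization visit, and record both readings. Where 4.3.1 requires acuity to be repeated after a delay, state what is used if only one reading exists.
2. Leave the better reading in place for eligibility, the continuation decision and the 2-line definition, and leave the first-test rule in 4.4.2 as it is.
3. Report within-arm change and 2-line rates with a note that baseline is the better of two tests and the 10-week value is a single test.

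The cost is one definition and one sentence in the report, with no extra testing and no change to the sample size. The downside is that the analysis covariate will differ from the value used for eligibility, and this needs to be stated.
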